5.5.7.3. Vital Signs

Vital sign parameters will be presented by time point, summarizing the actual values and change from Baseline to each on-treatment time point using descriptive statistics. A table summarizing the frequency and percent of subjects meeting the predefined markedly abnormal criteria at each visit will be presented. The predefined markedly abnormal criteria are defined below in Table 4. Vital signs data will be presented in the data listings.

Table 4 Predefined Markedly Abnormal Vital Sign Values

Variable	Units	Markedly Abnormal Criteria Lower limit	Markedly Abnormal Criteria Upper limit
Systolic blood pressure	mm Hg	<80	>130
Diastolic blood pressure	mm Hg	<40	>90
Pulse Rate	beats/min	<50	>130
Temperature	°C		≥40

5.5.7.4. 12-Lead ECGs

Electrocardiogram (ECG) parameters will be presented by time point, summarizing the actual values and change from Baseline to each on-treatment time point using descriptive statistics. A shift table will compare N (%) of ECG status at Baseline to the worst reported value through Week 96. A table summarizing the frequency and percent of subjects meeting the predefined markedly abnormal criteria at each visit will be presented. The predefined markedly abnormal criteria are defined below in Table 5. ECG data will be provided in a data listing.

Table 5 Predefined Markedly Abnormal Electrocardiogram Values

Variable	Units	Lower limit of normal	Upper limit of normal	Age Group (yrs)	Markedly Abnormal Criteria
Heart Rate	beats/min	50	120		
QTcF Interval	msec			All	Screening Visit >450
				<12	>480
				≥12	>500
				All	<320
					Increase >60
QRS Interval	msec			<12	IVCD or any QRS conduction disturbance
					with a QRS >110ms
				≥12	IVCD or any QRS conduction disturbance
					with a QRS >120ms
PR Interval	msec			<12	>190
				≥12	>220

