5.3. Clinical Experience with Eteplirsen

Two Phase 1 clinical studies of eteplirsen have provided initial support and proof-of-concept for the safety and potential efficacy of eteplirsen in the treatment of DMD. In light of the positive findings from the two Phase 1 studies, a 28-week, double-blind, placebo-controlled Phase 2 study (Study 4658-us-201) was initiated to assess efficacy, safety, tolerability, and pharmacokinetics (PK) of eteplirsen. Twelve patients aged 7 to 13 years were randomized to receive once-weekly intravenous (IV) infusions of eteplirsen (30 or 50 mg/kg) for 28 weeks, or once-weekly placebo infusions for 24 weeks followed by eteplirsen infusion (30 or 50 mg/kg) for 4 weeks. At Week 28, these same 12 patients were enrolled in the extension study (Study 4658-us-202) where they continued open-label eteplirsen at the same dose they were receiving upon completion of the parent study.

Two other eteplirsen studies are ongoing (Study 4658-203, a Phase 2 study in patients 4 to 6 years of age; and Study 4658-301, a Phase 3 confirmatory safety and efficacy study).

Based on the cumulative available safety data from these studies, eteplirsen has been shown to be well tolerated, with low rates of serious or severe adverse events (AEs). The following common AEs are categorized as adverse drug reactions given their frequency relative to placebo: headache, arthralgia, vomiting, nausea, upper respiratory tract infection, nasopharyngitis, and cough. In addition, the following events are also categorized as adverse drug reactions given their temporal relationship to eteplirsen administration: erythema, flushing, and mild temperature elevation.

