7.3. Study Endpoints

7.3.1. Safety Endpoints

Incidence of:

- Adverse events
- Clinical laboratory abnormalities
- Abnormalities in vital signs and physical examinations
- Abnormalities on electrocardiograms (ECGs) and echocardiograms (ECHO)

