10.3.2. Vital Signs and Weight

Vital signs (blood pressure, heart rate, respiration, and oral temperature) and weight will be measured at the time points specified in Section 2.

For infusion visits, vital signs are to be collected within approximately 30 minutes prior to infusion and approximately 5, 30, and 60 minutes after the end of the infusion. If the patient has not experienced an infusion reaction after the first year of treatment, vital signs may be collected only 30 minutes after the end of the infusion. All assessments will be performed after patients have remained seated for 5 minutes. Pulse rate and respiratory rate should be measured over 1 minute

Details about how weight measurements are obtained are provided in the Clinical Evaluator Manual. If a patient's weight varies by more than 10% from the prior visit, the patient should be re-weighed to confirm the result, and an explanation of the change should be documented.

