13.8.2.2. Physical Examination, Vital Signs, Weight, and Height/Ulnar Length

Vital signs, weight, and height/ulnar length will be presented by treatment condition and visit, summarizing the actual values and change from Baseline to each visit for each parameter using descriptive statistics. Frequency tables of predefined change abnormal in vital sign values will be generated.

Results from physical examinations will be presented in patient data listings.

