6. CHANGES FROM PLANNED ANALYSES

This SAP has made the following change to the planned analyses in the protocol (Amendment 1, 05 July 2016):

• Holter monitoring was to be summarized. It will instead be listed only.

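### The vital-sign abnormality table counts temperature only from 40 °C and no explicit pre- to post-infusion change is planned, so the table is practically blind to the mild temperature rise that the protocol names as an infusion-timed reaction

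*SAP*

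**What the plan says.** The protocol makes the incidence of "Abnormalities in vital signs and physical examinations" a safety endpoint (Protocol 7.3.1). Section 10.3.2 defines what is measured: "Vital signs (blood pressure, heart rate, respiration, and oral temperature) and weight will be measured". Around each infusion there is one reading within about 30 minutes beforehand and three afterwards, at about 5, 30 and 60 minutes. After the first year, patients with no infusion reaction may have the 30-minute reading only.

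Protocol 5.3 names certain events as "adverse drug reactions given their temporal relationship to eteplirsen administration: erythema, flushing, and mild temperature elevation".

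For the analysis, Protocol 13.8.2.2 states: "Frequency tables of predefined change abnormal in vital sign values will be generated". It gives no numeric limits. SAP 5.5.7.3 plans descriptive statistics, "summarizing the actual values and change from Baseline to each on-treatment time point using descriptive statistics", a per-visit count of patients meeting the Table 4 criteria, and a listing. Table 4 contains:

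- systolic pressure below 80 or above 130 mm Hg
- diastolic pressure below 40 or above 90 mm Hg
- pulse below 50 or above 130 beats/min
- temperature, upper limit only: "Temperature °C ≥40"

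SAP section 6 declares one departure from the protocol: "Holter monitoring was to be summarized. It will instead be listed only".

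**The concern.** Of the three infusion-timed reactions in Protocol 5.3, only temperature elevation is a vital sign, and the protocol calls it mild. The table that delivers the vital-sign incidence endpoint starts counting at 40 °C. A report that no patient had a markedly abnormal temperature would then say almost nothing about whether this known reaction occurred.

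Two features add to this. The protocol's wording points to criteria based on change, whereas Table 4 uses absolute limits only and omits respiration. And although a pre-infusion reading is scheduled, the visible SAP text never uses it as the reference for the readings that follow on the same day. Tolerability is part of the primary objective, so a per-patient count of measured post-infusion change is a natural thing for a reader to look for.

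**Working it through.** The plan gives no expected rate, power or precision for this endpoint, so there is no figure to reproduce. The check sets the texts side by side and adds an illustration on assumed values.

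**1. Distance to the temperature limit.** Rise needed = 40 − starting value. From assumed starting values of 36.5, 37.0 and 37.5 °C this is 3.5, 3.0 and 2.5 °C.

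**2. Chance that a raised reading is flagged.** Assume normally distributed readings with pre-infusion mean m of 36.5 to 37.0 °C, SD of 0.3 to 0.5 °C and rise r. Then p = 1 − Φ((40 − m − r)/SD), and the chance that at least 1 of 20 patients is flagged at one reading time is 1 − (1 − p)^20. The corner most favourable to the table (m = 37.0, SD = 0.5) gives:

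| Rise r | (40 − m − r)/SD | p | At least 1 of 20 |
|---|---|---|---|
| 1.0 °C | 4 | 0.00003 | 0.0006 |
| 1.5 °C | 3 | 0.0014 | 0.027 |
| 2.0 °C | 2 | 0.023 | 0.37 |

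Every other combination gives less; for example m = 36.5, SD = 0.5, r = 1.0 gives p = 0.0000003. Chances accumulate over readings, so take an extreme case: three post-infusion readings at all 96 infusions in 20 patients, 96 × 3 × 20 = 5,760, each raised by 1.0 °C. The expected number flagged is at most 5,760 × 0.0000317 ≈ 0.18.

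**3. Blood pressure and pulse.** From an assumed systolic pressure of 100 to 120 mm Hg, a fall of more than 20 to 40 mm Hg crosses 80. From an assumed pulse of 80 to 100, a rise of more than 30 to 50 beats/min crosses 130. The table therefore registers large excursions here. It does not register size of change as such: an illustrative systolic fall from 128 to 81 mm Hg (47) is not counted.

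**4. Protocol against SAP on change criteria.** Protocol 13.8.2.2, 13.8.2.3 and 13.8.2.4 use much the same phrase for vital signs, laboratory tests and ECG. The SAP answers it with change columns for chemistry (Table 3-2) and a QTcF increase above 60 msec (Table 5). For vital signs it supplies absolute limits only, and section 6 is silent on this.

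**5. Reference for change.** Protocol 13.1 generally takes Baseline as the last value before dosing. On that reading, change from Baseline may coincide with pre- to post-infusion change at the first infusion. At later visits it does not: by Week 96 the reference is 96/52 ≈ 1.8 years old, and the difference combines any infusion effect with whatever else has changed since.

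**The case against.** The strongest reply is that infusion reactions are already covered. SAP 5.5.7.1.1 has an Infusion Related Reactions group that includes pyrexia, raised body temperature, erythema, flushing and several hypotension terms, with a table and a listing. Signs seen by staff count as adverse events, and patients are observed for at least an hour after each infusion. This stands, and it rules out any inference that the plan ignores these effects. It is not a full substitute, because it depends on reporting: under Protocol 11.2.1 a test abnormality is an adverse event when it alters medical care, so a transient untreated rise may go unrecorded unless someone reports it as a sign or symptom.

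The time-point summaries also carry information. If pre- and post-infusion readings are separate time points, then in patients with both readings mean(post − Baseline) − mean(pre − Baseline) = mean(post − pre). A mean shift would show. What is lost is its spread and the number of patients affected.

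Table 4 is labelled as markedly abnormal, so excluding mild elevations may be deliberate. That explains the limit, but it leaves the incidence endpoint without a count for the named reaction.

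On change criteria, the protocol phrase is unclear and sets no limits, and the SAP's haematology criteria (Table 3-1) are almost entirely absolute too. A reader might infer that agreed criteria were dropped. The documents support only that a change-based table was not carried over and that this was not declared.

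**Conclusion.** The point holds in a limited form. The Table 4 count is practically blind to mild temperature elevation after infusion. Table 4 has no respiration row and no change criterion, with no declaration in section 6. The visible SAP text plans no explicit same-visit pre- to post-infusion change. The remaining routes (adverse event reporting, time-point summaries and listings) do not give a per-patient incidence of measured post-infusion change.

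Some stronger readings are tempting but not supported:

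- That the endpoint misses all the named infusion effects. Erythema and flushing are not vital signs, so no vital-sign table could count them.
- That large blood pressure falls go uncounted. Any value below 80 systolic or 40 diastolic counts.
- That a late change from Baseline mostly reflects growth and disease. The documents give no figure for the shares.
- That the timed readings are the only objective measure of tolerability, or that the pre-infusion reading is taken for this comparison. Neither is stated.

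The probabilities rest on assumed means, spreads and rises; the protocol does not define mild. At the most favourable corner, a 2.0 °C rise would be flagged in at least 1 of 20 patients with probability 0.37, so the conclusion applies to smaller rises. The reading of Baseline rests on Protocol 13.1, since the visible SAP has no definition and one may lie in text not available here. In a descriptive study of about 20 patients this is a cheap improvement, not a fault that undermines the safety analysis.

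**What to change.** In SAP 5.5.7.3:

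1. Keep change from Baseline, and add change from the same-visit pre-infusion reading to the 5-, 30- and 60-minute readings wherever the pre-infusion value was taken.
2. Add lower temperature reporting categories beside 40 °C, for example 38.0 °C or above and 39.0 °C or above.
3. Either add predefined change criteria for the vital signs, with a row for respiration, or state in section 6 that absolute limits replace the protocol's change-based table.

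These are reporting categories only; they use data already scheduled for collection and do not affect patient care. The cost is some SAP wording, a few table rows and more flagged values to read. After the first year the within-visit change may be unavailable for patients on reduced monitoring, so its tables should show how many patients contribute at each visit.

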13. STATISTICS

13.1. General Considerations

This section describes the rules, conventions, statistical analysis, and presentation of data for this study. Full details will be provided in the Statistical Analysis Plan (SAP) for this study.

Revisions during the study may be made to accommodate protocol amendments and to make changes to adapt to unexpected issues in study execution that could affect planned analyses. Any revisions will be based on blinded review of the data. A formal SAP for the analysis and presentation of data from this study will be prepared and issued before database lock. The SAP will provide a more technical and detailed description of the proposed data analysis methods and procedures. Deviations from the statistical analyses outlined in this protocol will be included in this plan; any further modifications will be noted in the clinical study report (CSR). All statistical analyses will be performed by or under supervision of the Sponsor.

All available data will be included in data listings and tabulations. No imputation of values for missing data will be performed. Percentages of patients with AEs or laboratory abnormalities will be based on nonmissing values.

All data collected in this study will be presented using summary tables and patient data listings. Summary statistics for raw and change from Baseline data of continuous variables will minimally include n, mean, standard deviation (SD), minimum, median, and maximum. For categorical variables, frequencies and percentages will be presented. Graphical displays will be provided as appropriate.

Endpoints will be assessed primarily using simple descriptive statistics and/or inferential statistics. Baseline will generally be defined as the last available value before dosing.

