- Screening ECG, Holter ECG, and ECHO may be performed at any time during the Screening period; however results must be available on Day 1, prior to dosing.
- g In the event of early termination prior to Week 96, the Week 96 assessments should be completed as the Early Termination Visit.
- ^h End of Study visit should occur within 4 weeks after last dose

Version 1.0 (20 April 2017) Page 11 of 40

Study Period					7	Гreatm	ent Per	riod					Safety Extension	End of Study ^h
Week	52	56	60	64	68	72	76	80	84	88	92	96/ET ^g	See Table 2	4 weeks after last infusion (as applicable)
Informed Consent														
Inclusion/Exclusion														
Medical History														
Full Physical Exam						X						X		X
Brief Physical Exam														
Vital Signs ^a	X	X	X	X	X	X	X	X	X	X	X	X		X
Weight	X	X	X	X	X	X	X	X	X	X	X	X		X
Safety Lab Assessments ^b						X						X		X
CCI														
Whole Blood (Genotyping/CCI) ^c														
Height and Ulnar Length						X						X		
CCI														
CCI														
ECG						X						X		
Holter ECG												X		
ЕСНО						X						X		
Study Drug Infusion							Once	Weekl	y					

Version 1.0 (20 April 2017)

Page 12 of 40

Study Period					7	[reatm	ent Per	iod				Safety Extension	End of Study ^h
Week	52	56	56 60 64 68 72 76 80 84 88 92 96/ET ^g last infusio					4 weeks after last infusion (as applicable)					
Conmed/Therapy		Continuous											
AE Assessment								С	ontinuo	us			

Footnotes for Table 1 Schedule of Events: Week 52 through End of Study

Functional assessments, \overline{CCI} , ECG, Holter ECG, and ECHO have a \pm 2 weeks window

- ^a For infusion visits, vital signs are to be collected within approximately 30 minutes prior to infusion and approximately 5, 30, and 60 minutes after the end of the infusion. If the patient has not experienced an infusion reaction after the first year of treatment, vital signs may be collected only 30 minutes after the end of the infusion.
- ^b Blood samples for the safety laboratory assessments must be obtained within 2 weeks prior to the Baseline/Week 1 visit, and results must be available prior to dosing at Baseline/Week 1. If more than 2 weeks have elapsed since the collection of blood samples for the Screening safety laboratory assessments, it must be repeated. If less than 2 weeks have elapsed since the collection of blood samples for the Screening safety laboratory assessments, additional safety laboratory assessments do not need to be performed.

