4.4.2 Demographics and Baseline Characteristics

- Age, race, ethnicity, weight, height, body mass index (BMI), genotype for column ambulatory status, and column will be summarized.
- Age will be calculated at date of first dose of eteplirsen at the Week 1 visit
- For the purposes of the demographic summaries, weight will be the last available measurement taken before the first study drug administration.
- BMI will be calculated as BMI = Weight (kg) / Height (m)². Any measurements in other units will be converted to kilograms and meters prior to the calculation. Weight (kg) = weight (lb)/2.2. Height (m) = height (inches)*0.0254.

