5.4.6 Definitions and Terminology

Study Day

Study day will be defined as Event Date – Study Day 1 + 1

Study Day 1

Day 1 is defined as the date of first dose of eteplirsen at the Week 1 visit during the 4658-204 Study.

Days on Study

Days on Study is the number of days from Study Day 1 to the date of study completion or early termination as recorded on the END OF STUDY VISIT CRF.

Days on Study Drug

Days on Study Drug is the number of days from the date of first dose to the date of the last dose of the specific study medication as recorded on the STUDY DRUG ADMINISTRATION CRF.

Planned Number of Infusions

The planned number of infusions will be based on the subject's last local site visit. The subject will be expected to receive an infusion once weekly up until their last local site

visit. If a subjects completes 100 local site visits and then completes or discontinues the study the planned number of infusions will be 100.

Treatment Group

All subjects received 30 mg/kg weekly of eteplirsen and will be analyzed in the same group.

Time Since DMD Diagnosis

The time since DMD diagnosis, in months, will be calculated as Month and Year of first dose – Month and Year of diagnosis

Treatment-Emergent Adverse Event

An AE is considered treatment-emergent if it occurs on or after the initiation of the first dose of eteplirsen and within 28 days of last dose.

Treatment Related Adverse Event

A treatment-related AE is any adverse event reported on the CRF that is marked as definitely, probably or possibly related to study drug. Additionally, it is assumed that an AE without a relationship is treatment-related.

Treatment-Emergent Laboratory Abnormality

[figure not shown]
A treatment-emergent laboratory abnormality is defined as any laboratory abnormality (as defined in section 5.5.7.2) that occurs following the initiation of eteplirsen which was not present at Baseline.

Prior Medication

A prior medication is any medication taken prior to the first study drug administration.

Concomitant Medication

A concomitant medication is any medication that is taken on or after the first study drug administration.

Final Analyses

An analysis will be performed once all subjects complete their End of Study visit and the resulting clinical database has been cleaned, quality checked and locked through the data cut.

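### SAP Table 5 applies the 450 ms QTcF limit at Screening only, so pre-dose and on-treatment abnormality counts may not compare like with like, and moderately raised on-treatment values go uncounted

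*SAP*

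**What the plan says.** SAP section 5.5.7.4 plans four ECG outputs:

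- Descriptive statistics, "summarizing the actual values and change from Baseline to each on-treatment time point using descriptive statistics".
- A shift table: "A shift table will compare N (%) of ECG status at Baseline to the worst reported value through Week 96".
- A threshold table: "A table summarizing the frequency and percent of subjects meeting the predefined markedly abnormal criteria at each visit will be presented".
- A data listing.

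The threshold table uses Table 5, which gives five QTcF criteria:

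| Criterion (ms) | Age group | Visit label |
|---|---|---|
| >450 | All | Screening Visit |
| >480 | <12 | none |
| >500 | ≥12 | none |
| <320 | All | none |
| Increase >60 | not given | none |

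The first row reads "Screening Visit >450". It is the only criterion in SAP Tables 3-1 to 6 that is tied to a visit.

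The schedule (SAP section 4.3, Table 1) marks an ECG at Screening and none at Baseline/Week 1. A footnote allows flexible timing: "Screening ECG, Holter ECG, and ECHO may be performed at any time during the Screening period", with results required before dosing. Protocol section 13.1 states: "Baseline will generally be defined as the last available value before dosing". The Screening ECG is therefore normally the Baseline ECG.

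**The concern.** ECG abnormalities are a protocol safety endpoint (Protocol 7.3.1). The study has one arm, so a reader of the threshold table will naturally set the pre-dose percentage beside the on-treatment percentages. If the two are judged against different limits, the difference between them partly reflects the limits and not the patients.

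The lower limit applies before dosing, so the lean is towards the drug looking neutral or favourable on QTcF. Separately, the table has no absolute category for an on-treatment value that is above 450 ms but not above the age-specific limit. Such a value would have been counted at Screening.

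**Working it through.** The plan states no figure to reproduce: there is no formal sample size calculation and no QTcF mean or SD.

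**Gap between limits.** 480 − 450 = 30 ms (<12 years); 500 − 450 = 50 ms (≥12 years).

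**Fixed cases.** These apply the Table 5 rules directly and need no distribution.

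| Screening → on treatment (ms) | Change | Flag at Screening | Flag on treatment |
|---|---|---|---|
| 455 → 455 | 0 | yes | no, either age group |
| 455 → 480 | +25 | yes | no, either age group |
| 455 → 490, age ≥12 | +35 | yes | no |
| 445 → 499, age ≥12 | +54 | no | no |
| 445 → 499, age <12 | +54 | no | yes (499 > 480) |
| 400 → 465 | +65 | no | yes (increase > 60) |

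The first three rows show the lean. The last shows that it can reverse: if all 20 patients moved this way, the counts would be 0/20 at Screening and 20/20 on treatment.

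**Expected counts with no drug effect.** Assumptions: 20 patients, normal QTcF, one Screening and one on-treatment ECG each, one combined flag per visit. Screening flag: >450 or <320. On-treatment flag: above the age limit, <320, or increase >60.

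Expected Screening count from the high limit = 20 × P(Z > (450 − mean)/SD):

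- Mean 400, SD 15: z = 3.33, 20 × 0.0004 = 0.01
- Mean 410, SD 20: z = 2.00, 20 × 0.0228 = 0.45
- Mean 420, SD 25: z = 1.20, 20 × 0.115 = 2.30

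On treatment, the increase criterion adds chance flags. With within-patient SD 15, the SD of a change is 15 × √2 = 21.2, and 20 × P(Z > 60/21.2) = 20 × 0.0023 = 0.05. Simulation of the full rules gives:

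| Mean / SD / within-patient SD | Screening | On treatment, <12 | On treatment, ≥12 | Chance of strictly fewer flags on drug |
|---|---|---|---|---|
| 400 / 15 / 10 | 0.01 | 0.00 | 0.00 | 0.01 |
| 410 / 20 / 15 | 0.45 | 0.05 | 0.05 | 0.35-0.36 |
| 420 / 25 / 15 | 2.30 | 0.20 | 0.06 | 0.88-0.90 |

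Most of the remaining probability is ties.

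**With a true shift.** Across these scenarios, the chance of more flags on drug than at Screening is 0.29-0.73 for a 30 ms shift and 0.96-0.999 for 50 ms.

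**With >450 at every visit** (keeping <320 and increase >60). With no drug effect, Screening and on-treatment counts agree: 0.45 and 0.48 in the second scenario, 2.30 and 2.32 in the third. With a 30 ms shift, the on-treatment counts are:

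| Scenario | Table 5, <12 | Table 5, ≥12 | >450 at every visit |
|---|---|---|---|
| 410 / 20 / 15 | 1.84 | 1.59 | 6.65 |
| 420 / 25 / 15 | 3.35 | 1.88 | 10.31 |

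**The case against.** - **The layout is not stated.** The SAP does not say that Screening is a column, or that the criteria form one combined flag. With separate rows, >480, >500 and <320 compare like with like, and >450 is an extra row at Screening. This stands, and it makes the comparability problem conditional. It does not remove the uncounted on-treatment band, which exists under either layout.
- **The >450 row may be an entry check.** Inclusion criterion 4 and exclusion criteria 8 and 10 are redacted, so a QTcF entry limit cannot be ruled in or out. If there were one at 450 ms, few or no enrolled patients would be flagged at Screening and the apparent improvement would largely vanish. This stands as a limit on size.
- **Other outputs show QTcF.** A rise of 35 or 54 ms enters the change-from-Baseline summary and is visible in a listing of about 20 patients. This stands and lowers the stakes. Those outputs do not count patients above a threshold, though. The shift table stops at Week 96 while ECGs continue at Weeks 120 and 144, and section 5.5.7.4 does not define ECG status.
- **Where to set markedly abnormal is a choice.** That is fair, but it does not explain using one absolute limit before dosing and another after.

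A reader might also infer a bias from age, since the limits change at 12 years and the SAP says "Age will be calculated at date of first dose of eteplirsen at the Week 1 visit". The documents do not support that. The sentence belongs to the demographics section and is not linked to Table 5. A patient who kept the under-12 limits after turning 12 would face stricter limits, giving more flags on drug.

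**Conclusion.** The point holds in a limited form. Table 5 ties the 450 ms limit to the only scheduled pre-dose ECG and leaves no matching category on treatment.

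- **Conditional:** if Screening is shown under a combined flag, pre-dose and on-treatment percentages are not comparable and lean towards fewer absolute-limit flags on drug.
- **Unconditional:** on-treatment values of 451-480 ms (<12) or 451-500 ms (≥12) are not counted unless the increase exceeds 60 ms.

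A reader might infer that the table must show fewer abnormal patients on drug than before it. It need not, because the increase criterion can be met only after Baseline and the counts can tie or reverse.

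The size cannot be fixed from the documents. The range of about 0 to 2 of 20 flagged at Screening rests on assumed means of 400-420 ms and SDs of 15-25 ms; the 30 and 50 ms gaps and the fixed cases rest on no such assumption. The other ECG outputs limit the harm, but the table should still be corrected.

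**What to change.** In SAP Table 5, remove the Screening Visit restriction. Count QTcF >450, >480 and >500 ms as separate rows, each with the same cut-off at Screening and at every later visit. Give the increase >60 ms and <320 ms criteria their own rows. State in section 5.5.7.4 that Screening is a displayed column. If >450 ms was an entry check, report it in the eligibility listing (section 5.5.1) as well. This point needs no change to how age is assigned; switching to age on the ECG date would raise a patient's QTcF limit by 20 ms (480 to 500) during treatment.

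The cost is SAP wording and a few extra rows in one table, with no new data. More on-treatment values will be counted, which may look slightly less favourable to the product.
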